#### 2.7 Inclusion Criteria

Inclusion criteria includes: patients  $\geq$  18 years of age admitted to the Surgical Unit who are experiencing an initial episode of nausea status post laparoscopic sleeve gastrectomy or laparoscopic Roux-En-Y (RNY) surgery and/or revisional bariatric surgery; must be able to read and speak English; able to follow directions; not allergic to peppermint, spearmint, ginger and/or lavender; bariatric surgeon is part of IMG group and patient is an inpatient.

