## 1. INTRODUCTION

#### 1.1 Specific Aims

The use of integrative approaches to health and wellness has grown within care settings across the United States. Integrative health is when complementary approaches are utilized in mainstream health care (National Center for Complementary and Integrative Health (www.nccih.nih.gov; Downloaded 2/7 /19, Complementary, Alternative, or Integrative Health: What's In a Name).

Aromatherapy is one type of complementary approach. It is the use of essential oils for the purposes of healing. It has been used for years to relieve pain, promote healing, kill bacteria, and maintain health. It has been accepted as a part of nursing in many countries but only recently has been a part of nursing in the United States. Clinical aromatherapy is the use of essential oils for specific, measurable outcomes (Kreitzer 2014 - book). Certain essential oils (lavender, lavandin, mandarin, rose, bergamot, and frankincense) have their own relaxing properties and all have been shown their potential to reduce stress (Buckle, 2015).

Primary Aim: To determine the effectiveness of using aromatherapy as a first line intervention in place of an antiemetic in post-operative bariatric patients who experience nausea on the surgical unit at IFOH.

Secondary Aim: To determine if aromatherapy utilization for the treatment of post-operative nausea is more effective with a particular post-operative bariatric patient population (sleeve gastrectomy, Roux-En-Y, revisional bariatric surgery) on a surgical unit than with another.

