# 2.8 Exclusion Criteria

Exclusion criteria include: patients < 18 years of age; non-English speaking; not able to follow directions; inability to smell (anosmia); allergy to peppermint, spearmint, ginger and/or lavender; receiving bariatric surgery for gastroparesis; pregnant or breastfeeding; vulnerable subjects; receiving complementary therapy (healing touch, music therapy) or presently enrolled in another research study.

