# 3 STUDY METHODS AND PROCEDURES

#### 3.1 Study Treatment/Intervention

Once consent is obtained, the licensed prescriber will enter an order into the patient's electronic medical record (EMR) for the aromatherapy product. It will be a one-time order to administer the aromatherapy product for complaints of nausea while on the surgical unit for the first 24 hours post-operatively. This order will appear on the medication administration record (MAR) in the EMR.

Pharmacy will review and release the aromatherapy order. Pharmacy will be provided with the study Subject Identification (SID) number, a copy of the patient's research consent and randomization scheme generated by SAS which will determine the protocol drug (aromatherapy product A or B). Pharmacy will apply a patient label to study drug and one label on the delivery sheet. The pharmacy will dispense the study drug to the Surgical Unit. The study drug will be placed in the patient's medication bin in the medication room closet to the patient's room. Pharmacy will maintain all delivery sheets in a secure location.

If the enrolled post-operative bariatric patient complains of nausea for first time (initial) while on the surgical unit within the first 24 hours post-operatively, the participant will be offered a one-time aromatherapy intervention with either product A or product B (based on the randomization scheme) for their nausea treatment. A member of the research team will instruct the patient on the use of the QueaseEASETM aromatherapy product (A or B) and also provide them with the educational handout (refer to appendix F: Aromatherapy patient education sheet). The instructions to use are the same for product A as product B.

The direct care nurse will assess the patient's nausea level prior to the intervention. The direct care nurse will provide the patient with their randomized product, and the patient can utilize the product for up to 5 minutes. The nurse will document this one time aromatherapy administration via the MAR. The nurse or a member of the research team will then reassess the patient's nausea level at 5 minutes.

After the aromatherapy intervention the nurse will remove and discard the patient label from the study drug and dispose of the study drug in the appropriate receptacle.

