#### 3.4 Endpoints/Outcomes Measurements

# 3.4.1 Primary outcome.

Primary end-point: Post-operative bariatric patients that use aromatherapy will have a greater decrease in mean nausea levels compared to control group.

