# 4.2 Method of Data Analysis

Data will be presented as mean ± SD or frequency (percent), where appropriate. Group differences will be compared using Student's t-test, or chi-square tests of association, where appropriate. Data will be assessed for departures from normality with group comparisons adjusted accordingly. The primary hypothesis efficacy endpoint is incidence rate of nausea following surgery. Rates of nausea and 95% confidence intervals will be presented and group comparison will be via chi-square tests. The primary efficacy analysis will only include surgery groups sleeve gastrectomy and Roux-En-Y. However, to expand our knowledge regarding the effect of aromatherapy, we will recruit patients undergoing revisional bariatric surgery but these will only be considered for secondary analyses. As this is an RCT, we anticipate potential cofounders (e.g., gender, type of surgery, etc.) and effect modifiers to be distributed equally. However, in the event of a failed distribution of clinical or demographic characteristics, mixed effects modeling will be substituted to test the primary hypothesis. All analyses will be conducted using SAS (Ver.9.4, Carey, NC) with statistical significance considered as p≤0.05, two-tailed.

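### PACU antiemetic use is recorded in Appendix H but has no prespecified place in the nausea or antiemetic-use comparisons

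*Combined protocol and SAP*

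**What the plan says.** **Entry.** Section 2.7 requires patients "admitted to the Surgical Unit who are experiencing an initial episode of nausea status post laparoscopic sleeve gastrectomy" or one of the other listed operations. Section 3.1 offers the product when an enrolled patient "complains of nausea for first time (initial) while on the surgical unit within the first 24 hours post-operatively". The index event is therefore the first nausea on the unit, not the first after surgery. The only exclusion in section 2.8 that concerns concurrent treatment is for patients "receiving complementary therapy (healing touch, music therapy) or presently enrolled in another research study". No section sets a condition on an earlier antiemetic or a minimum interval since one.

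**Measurement.** Nausea is scored 0–3 just before the product. Section 3.1 continues: "The nurse or a member of the research team will then reassess the patient's nausea level at 5 minutes".

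**Data.** The Appendix H sheet asks whether an antiemetic was received in PACU and, if so, its name, dose and time.

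**Analysis.** Under section 3.4.1, aromatherapy patients "will have a greater decrease in mean nausea levels compared to control group". Section 4.2 instead states: "The primary hypothesis efficacy endpoint is incidence rate of nausea following surgery", to be compared by chi-square. On baseline factors, section 4.2 says "we anticipate potential cofounders (e.g., gender, type of surgery, etc.) and effect modifiers to be distributed equally", and that mixed effects modelling replaces the planned test if clinical or demographic characteristics turn out unevenly distributed. The Abstract's statistical paragraph says the same. PACU antiemetic is not named in any of these places. Sections 3.3 and 4.1 do not describe randomisation stratified by it.

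**The concern.** A patient who was nauseated and treated in PACU can qualify on the unit while that drug is still acting. Part of the 5-minute change could then come from the drug, and the same exposure could plausibly affect antiemetic use over the next 24 hours, which is a secondary endpoint. The study collects the variable that would describe this and then gives it no role.

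Three things are at stake:

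- Precision, if PACU treatment is related to outcome.
- How a chance difference in PACU treatment between arms is handled. Section 4.2 leaves this to a judgement made after the data are seen, with no threshold, variable list or model.
- Whether the product works differently in patients already treated in PACU. The plan provides no breakdown that would show this.

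**Working it through.** **Inputs from the documents.** Control nausea rate 80%, a 20% reduction, 90 per arm, 5% alpha, 1:1 allocation and a loss allowance of 30 (section 4.1); two-tailed testing (section 4.2).

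**Assumptions, because the documents give no figure.** Share of patients with a PACU antiemetic, q = 20–60%. Carry-over, c = 10–30 percentage points lower nausea at 5 minutes.

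**1. The plan's own power.** For 80% v 60%, with pooled rate 0.70:

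z = (0.20 − 1.96 × sqrt(2 × 0.70 × 0.30 / 90)) / sqrt((0.80 × 0.20 + 0.60 × 0.40) / 90) = (0.20 − 0.134) / 0.0667 = 0.99

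Power is 83.9%, so the claim of at least 80% reproduces when the reduction is read as absolute. Read as relative (80% v 64%), power is 66.9%. The absolute reading is used below.

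**2. Equal carry-over in both arms.** The rates become 0.80 − qc and 0.60 − qc, so their difference stays at 0.20. Power at 90 per arm is 82.6% (q = 20%, c = 10 points) down to 77.0% (q = 60%, c = 30 points). Simulated type I error with c = 30 points is 0.049–0.053. Validity is intact and some power is lost.

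**3. Precision that adjustment could recover.** The share of outcome variance due to PACU status is 2q(1 − q)c² divided by the sum over arms of p(1 − p).

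- q = 40%, c = 30 points: 2 × 0.24 × 0.09 / (0.68 × 0.32 + 0.48 × 0.52) = 0.0432 / 0.4672 = 9%.
- q = 40%, c = 10 points: 2 × 0.24 × 0.01 / (0.76 × 0.24 + 0.56 × 0.44) = 0.0048 / 0.4288 = 1%.

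**4. Chance imbalance.** SD of the difference between arms = sqrt(2q(1 − q) / n).

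| q | n per arm | SD | z for 10 points | P(gap ≥ 10 points) |
|---|---|---|---|---|
| 20% | 90 | 0.060 | 1.68 | 0.09 |
| 40% or 60% | 90 | 0.073 | 1.37 | 0.17 |
| 40% or 60% | 75 | 0.080 | 1.25 | 0.21 |

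The last row uses the loss allowance: (180 − 30) / 2 = 75 per arm.

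**5. What an imbalance does to the result.** Shift = gap × c. A 10-point gap with c = 30 points gives 0.10 × 0.30 = 0.03. At the 95% limit of the gap (0.117 to 0.143 at 90 per arm) the shift is 0.035 to 0.043. The planned difference is 0.20 and its standard error is 0.067 (step 1).

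**6. If the effect differs by PACU status.** As an extreme illustration, suppose the product adds nothing in PACU-treated patients. The overall difference is then 0.20 × (1 − q).

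| q | Difference | Power at 90 per arm |
|---|---|---|
| 20% | 0.16 | 62–65% |
| 40% | 0.12 | 38–42% |
| 60% | 0.08 | 19–21% |

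Nothing in the documents says that this happens. It shows what the planned analysis could not reveal.

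**The case against.** The strongest reply is that the trial is randomised against placebo and tests a difference between arms. PACU dosing happens before the product is used, so the product cannot cause it, and it is balanced in expectation. The test's standard error already allows for chance differences. This stands. A reader might infer that drug carry-over biases the 5-minute comparison; steps 2 and 5 show that it does not do so systematically. The baseline score also follows any PACU dose, so only further drug effect within those 5 minutes can count. No interval between dose and product is given, and no document says how strongly PACU treatment predicts outcome.

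A second reply is that section 4.2 already provides for imbalance, through an open-ended list of characteristics that could include this one. That is partly right: imbalance is not simply ignored. But the rule works only after the data are seen and does not say what would trigger it.

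Two other inferences fail:

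- That calling the inhaler "using aromatherapy as a first line intervention in place of an antiemetic" is untrue for PACU-treated patients. The aim in section 1.1 goes on to limit itself to nausea on the surgical unit, so it can be read as first line for that episode.
- That a unit antiemetic given before the product is lost. Appendix H times the first unit antiemetic and Form A times the product, so the order can be recovered.

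Finally, a plain chi-square takes no covariate, so adjustment changes the primary test. That is a real cost.

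**Conclusion.** The point holds as a minor, inexpensive improvement. A pre-product variable that may be prognostic is collected, and no prespecified analysis uses it. This does not invalidate the randomised comparison.

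On the assumed ranges, adjustment would remove roughly 1–9% of the outcome variance at 40% PACU use. A 10-point imbalance would occur in about 9–17% of trials with 90 per arm, and would move the risk difference by about 0.03 if carry-over were as large as 30 points. These sizes rest on assumed PACU rates and carry-over. The larger power losses in step 6 need the further assumption that the product does nothing in PACU-treated patients, and should not be read as expected. The effect on the 24-hour antiemetic endpoint cannot be sized from the documents.

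The gap is the same whether mean change (section 3.4.1) or incidence (section 4.2) is kept as primary.

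**What to change.** In section 4.2, and in the matching paragraph of the Abstract:

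- Prespecify PACU antiemetic (yes/no) as an adjustment variable in the nausea comparison. For mean change, use it as a covariate in a linear model. For the binary endpoint, use a Mantel-Haenszel analysis stratified by it, or a logistic model that includes it.
- Use the same variable in the comparison of 24-hour antiemetic use.
- State that this replaces conditional adjustment for this variable.
- Report the treatment effect descriptively, with confidence intervals, in patients with and without a PACU antiemetic.

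Adjustment is more practical than stratified randomisation, because PACU treatment is not known when patients are randomised at enrolment. The variable is already on the Appendix H sheet, so no new data item is needed, and eligibility and care are unchanged.

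**Cost.** The primary test becomes stratified or model-based instead of a plain chi-square or t-test. The subgroup estimates will be imprecise: at an assumed 40% PACU use there are 0.40 × 90 = 36 treated patients per arm, which gives a 95% half-width of 1.96 × sqrt(0.40 / 36) = 0.21 and about 46% power for 80% v 60%. They should be labelled descriptive.

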#### **Study Methodology:**

Subjects will be provided with information about this research study by the following means: a member of the research team (IMG Nurse Practitioners) will discuss the research study during the patient's second pre-operative visit; study information will be uploaded to their MyChart portal; and flyers will be available in the IMG office (refer to appendix A: IMG office flyer). Interested patients will be able to fill out a brief form (refer to appendix B: Interested patient card) requesting to be contacted for further information, this form will be placed in a secure box at the reception desk or the patients can indicate interest by contacting one of the research team members. A member of the research team may need to access medical record information in order to confirm potential patient's phone number and or email address for further contact. A member of the research team will contact any interested patients and answer any questions regarding the research study. Consent will be obtained while the patient is in the peri-operative holding area on day of surgery by a member of the research team, excluding the IMG Nurse Practitioners. The research team member will determine if the patient is eligible for the study, discuss the study, answer any questions, and obtain consent (refer to appendix C: Consent). All members of the research team have completed Informed Consent Training. Once the consented post-operative bariatric patient complains of initial nausea on the Surgical Unit, the direct care nurse or research team member will ask the patient to rate their nausea level using a VAS on a 0-3 scale. Patients will be provided with either product A or B based on randomization scheme calculated by SAS (ver.9.4, Cary, NC). The patient will receive a one-time aromatherapy intervention. Nausea levels will be reassessed 5 minutes after the aromatherapy intervention. If the nausea level does not improve after the study drug intervention an antiemetic medication will be offered (refer to appendix D: Data Collection Form A).

On day of discharge a member of the research team will ask the patient the following questions regarding the Aromatherapy QueaseEASETM product (refer to appendix E: Data Collection Form B). The study will occur Monday through Thursday.

Did you use the QueaseEASE IM product?	Yes N	No	
If yes: How beneficial was the aromatherapy?	0 1 2 no benefit	3 4 5 very bene	eficial

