A 2014 prospective randomized two group design study conducted by Hodge, McCarthy, & Pierce compared the use of QueaseEASETM versus an unscented inhalant in relieving PONV on a surgical unit for the first 24 hours. Three hundred and thirty nine patients were enrolled and 112 patients experienced PONV, the 112 subjects were randomized into the treatment group (QueaseEASETM inhaler) and control group (placebo inhaler). Findings were the following: perceived effectiveness of aromatherapy was significantly higher in the treatment group (p<0.001) and there was a significant difference between the two groups (p=0.03). Hodge and colleagues (2014) noted that the nurse is not always able to respond as promptly as the patient desires in regards to the administration of antiemetic medication. The aromatherapy device is immediately available for the patient and if it does not completely relieve PONV, it may help the patient during the waiting time for the antiemetic to be administered. Asay (2018) conducted a systematic review of the literature regarding the use of aromatherapy in postoperative nausea and vomiting, and the synthesis of evidence did support the use of aromatherapy for PONV. Asay and colleagues stated the following "aromatherapy has a positive effect on PONV, and therefore should be considered as a complementary therapy or as an adjunct to antiemetic medications" (p. 1).

Hudgen, Hunt, Dienemann, Norton and Hartley (2013) conducted a randomized control trial of three aromatherapy agents (ginger, isopropyl alcohol and a blend of essential oils). Normal Saline was used as the control. The purpose of the study was to investigate the effectiveness of aromatherapy agents on the treatment of PONV for patients after surgery. Sample size was 301 subjects, who were randomly given one of the four agents upon initial complains of PONV via a gauze pad and instructed to inhale the aroma. Findings included: change in nausea was most significant for the aromatherapy blend agent (p=0.0001), then the ginger agent (p=0.0006) and there was no significant finding for isopropyl alcohol compared to NS. The number of antiemetic medication that was requested after the blended aromatherapy intervention was reduced.

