#### 3.3 Randomization

Upon enrollment in the trial, each subject will be randomized to one of two treatment groups: Product A (aromatherapy inhaler product), Product B (Placebo product: inhaler with distilled water). Each product will look the same. SAS will be used to generate the randomization table using random numbers to determine which treatment subject #1 will receive; subject #2 will receive, etc., resulting in a total of 90 subjects for each treatment group. The randomization scheme will be located in a secured location in the pharmacy department and access will be granted to Pharmacy and designated research team members.

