#### 3.5 Consent/Assent

Informed written consent will be obtained by either the PI or SI. The PI or SI will provide consent document to all willing participants after they have met the inclusion criteria listed above and have not met any exclusion criteria. The participant will have an opportunity to view the consent, read the contents, and have time to ask any questions. If they are willing to be a participant in the study the consent will be signed and witnessed by the PI or SI. See attached Informed Consent Document from potential participants (refer to appendix C: Consent).

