# 4 STATISTICAL CONSIDERATIONS/DATA ANALYSIS

# 4.1 Sample Size

To test the primary hypothesis that aromatherapy will lead to a decrease in post-operative nausea among patients undergoing laparoscopic/robotic sleeve gastrectomy, Roux-En-Y, and/or revisional bariatric surgery we will use a Pearson Chi-Square test for proportion difference. Assuming an expected incidence of nausea among controls of 80%, an alpha level of 5 percent, and a 1:1 treatment to control group ratio, we anticipate 90 subjects per group (n= 180 total) provides at least 80% power will to detect a statistically significant 20% reduction in the incidence of nausea among aromatherapy patients. The randomization scheme was calculated with SAS (ver.9.4., Cary, NC) using a two-group (treatment vs. placebo), simple randomization block (n=15) design. The total randomization scheme was increased to 180 (15 blocks of 12 patients) to allow for drop out and screen failures. Sample size will be increased to 180 subjects, this allows for a 20% (n=30) adm/screen fail/etc. error.

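### Nausea on the unit is an inclusion criterion but allocation comes before it, so the 90 per arm behind the power claim counts patients randomised, not patients evaluable

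*Combined protocol and SAP*

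**What the plan says.** **Eligibility.** Section 2.7, and the abstract's Study Design paragraph, require patients on the surgical unit "who are experiencing an initial episode of nausea". Section 3.5 has the consent document given to patients "after they have met the inclusion criteria listed above".

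**Consent and allocation.** The abstract's Study Methodology says: "Consent will be obtained while the patient is in the peri-operative holding area on day of surgery". Section 2.2 agrees. Section 3.3 says: "Upon enrollment in the trial, each subject will be randomized to one of two treatment groups". Section 3.1 continues: "Once consent is obtained, the licensed prescriber will enter an order into the patient's electronic medical record (EMR) for the aromatherapy product". Pharmacy then uses the randomisation scheme to dispense product A or B to the unit.

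**Use.** Under section 3.1 the product is offered only if the enrolled patient "complains of nausea for first time (initial) while on the surgical unit within the first 24 hours post-operatively". Nausea is scored before use and again at 5 minutes.

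**Size.** Section 4.1 states: "we anticipate 90 subjects per group (n= 180 total) provides at least 80% power". The same section says the list was raised to 180 to cover drop-outs and screen failures, an allowance of 30. Section 3.3 randomises 90 to each arm.

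**Analysis.** Section 4.2, and the abstract's Statistical Methodology, confine the primary efficacy analysis to sleeve gastrectomy and Roux-En-Y. Revisional patients are recruited but enter secondary analyses only. Neither place says whether a randomised patient who never becomes nauseated is in the primary denominator.

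**The concern.** Nobody in the holding area before surgery can meet a criterion of current nausea on the post-operative unit. Sections 2.7 and 3.5 therefore cannot be applied alongside the consent and dispensing steps. In practice, allocation precedes the event that defines who is treated and scored.

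Two things are at stake. First, the 90 per arm in the power statement is the number allocated. The number with an outcome that the inhaler could affect will be smaller, by an amount the plan does not estimate. Second, with no analysis set defined, the primary denominator could be settled after the data are seen.

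**Working it through.** **Inputs from section 4.1:** Pearson chi-square test, control rate 80%, reduction 20%, alpha 5%, 1:1 allocation, 90 per arm. Section 4.2 makes the test two-tailed. Whether the 20% is absolute or relative is not stated.

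**Formula** (pooled variance, n per arm, no continuity correction):

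power = Φ{ [ |p1 − p2| − 1.96·√(2·p̄(1 − p̄)/n) ] / √( [p1(1 − p1) + p2(1 − p2)]/n ) }

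With p1 = 0.80, p2 = 0.60 and p̄ = 0.70, we have 2·p̄(1 − p̄) = 0.42 and p1(1 − p1) + p2(1 − p2) = 0.16 + 0.24 = 0.40.

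**Reproducing the plan.** At n = 90: √(0.42/90) = 0.0683 and √(0.40/90) = 0.0667. Then (0.20 − 1.96 × 0.0683)/0.0667 ≈ 0.99, and Φ gives 83.9%. The claim of at least 80% reproduces on the absolute reading, provided all 90 per arm are evaluable. The relative reading (80% v 64%) gives 66.9% at 90 per arm and does not reproduce it, so the absolute reading is used below.

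**Evaluable number under different losses:**

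| Situation | Evaluable per arm | Power |
|---|---|---|
| Everyone randomised is evaluable | 90 | 83.9% |
| Smallest number reaching 80% | 82 | 80.4% |
| One fewer | 81 | 79.9% |
| Plan's allowance: (180 − 30)/2 | 75 | 76.7% |
| 80% become nauseated (assumed): 0.80 × 90 | 72 | 75.0% |
| One-third become nauseated (low end): 90/3 | 30 | 39.1% |

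**Threshold.** 82/90 = 91.1%, so power stays at 80% or above only if no more than about 9% are lost. The allowance of 30 is 30/180 = 16.7% of the list and already exceeds that. (30 is 20% of 150, which is how section 4.1 describes it.)

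**Low end.** Section 1.3 reports of an earlier surgical-unit trial of the same product: "Three hundred and thirty nine patients were enrolled and 112 patients experienced PONV". That is 112/339 = 33.0%. The same section gives one-third for post-operative patients generally.

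**Not computed.** The number of revisional patients is not given, so the further loss from excluding them cannot be sized. The allowance and the 80% scenario have not been stacked, because section 4.1 does not say whether its allowance is meant to include patients without nausea.

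**The case against.** - **The plan does allow for losses.** Because nausea is an inclusion criterion, a patient who never has it could count as a screen failure, which section 4.1 covers. This is a fair reading, and it keeps the shortfall modest. It does not remove the shortfall, because 180 is already the enlarged total and taking out 30 leaves 76.7%.
- **Section 4.1 says subjects, not treated subjects, and 82 per arm is enough.** This stands. A reader might infer that 180 randomised can never deliver 80% power. The documents do not support that: if 91% or more were evaluable, the claim would hold, and the nausea frequency on this unit is not given.
- **The one-third rate is too pessimistic.** This also stands. A reader might take 39% as the trial's likely power. The cited trial is not described as bariatric, and section 1.3 itself says general anaesthesia and laparoscopy, both used here, raise the risk. One-third marks the low end of a range.
- **The endpoint in section 4.2 is incidence of nausea after surgery, so all 180 count.** An inhaler used only after nausea starts cannot change whether it starts, so 80% v 60% makes sense only as nausea remaining in treated patients. A reader might go on to dilute both rates with never-nauseated patients and report still lower power. That relies on one reading of the 80%. If it is the incidence among all controls, as worded, those patients are already inside it.
- **Randomisation before surgery is inferred.** This is correct, since no clock time is given. The recruitment script ties receipt of the product to first nausea, but that describes receipt, not assignment. The point needs only that assignment precedes nausea, which sections 3.1 and 3.3 show.

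**Conclusion.** The point holds in limited form. Sections 2.7 and 3.5 contradict the consent, randomisation and dispensing steps, and the primary denominator is undefined. The power statement treats the number randomised as the number evaluable. On the plan's own allowance, power is 76.7% rather than at least 80%. If 80% of patients become nauseated it is 75.0%. Both figures are before revisional patients are removed.

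These figures assume an absolute 80% v 60% contrast, two-sided 5% alpha and no continuity correction. They follow the proportion endpoint of sections 4.1 and 4.2. Section 3.4.1 instead names mean change in nausea level, and the documents give no inputs for sizing a trial on that. The nausea frequency is an assumption throughout, and the shortfall is a few percentage points unless it is well below 80%.

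**What to change.** 1. **Sections 2.7 and 3.5.** Reconcile them with section 3.1 by separating pre-operative enrolment criteria from the post-operative event, already described in 3.1, that triggers use of the product.
2. **Section 4.2.** Define the primary analysis set as all randomised sleeve gastrectomy and Roux-En-Y patients who report first nausea on the unit within 24 hours, analysed by assigned arm whether or not the inhaler was used. Keep revisional patients in secondary analyses as planned, and report the never-nauseated count by arm. Because the trigger precedes exposure, this restriction keeps the arms comparable only if knowledge of the allocation cannot influence who is recorded as nauseated. Section 2.3 identifies product A as active and Form A records the product letter, so state that the code is concealed from unit staff until the baseline nausea score is recorded.
3. **Section 4.1.** State the number randomised and the number expected to be evaluable separately. Give the assumed nausea frequency with a range, and restate power for the evaluable number (about 75–77% at 72–75 per arm, before removing revisional patients).

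The cost is protocol wording and a less favourable power figure, with no extra patients. This reports the shortfall and does not cure it. If the sponsor wants to keep 80% power, 82 evaluable per arm at an assumed 80% nausea frequency means randomising 164/0.80 = 205, before other losses and the revisional exclusion.
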